### Quantitative Data Analyses (Aim 3)

We will conduct multilevel longitudinal data analyses to examine change in psychosocial outcomes. Time will be coded as 0, 1, and 2 respectively for pretreatment, posttreatment, and 1-month follow-up; therefore, the Level-1 intercept will represent initial status and the Level-2 time coefficient will represent change over time. We will also evaluate a model using linear and quadratic polynomial contrasts and orthogonal contrasts to evaluate non-linear (i.e., non-constant) change. We will add a dummy-coded intervention variable (RISE vs. information/referral condition) as a predictor of the Level-1 change parameters (initial status and change over time) to evaluate the treatment x time interaction (i.e., does group membership moderate change in the outcomes?). This analytic strategy will produce effective and efficient tests of change in outcomes, even in the presence of attrition, and provides us with flexibility to assess and adjust for control variables, if needed (e.g., age, IPV frequency). We will calculate effect size estimates and 95% confidence intervals, which produce an estimate of  $d$  from multilevel analyses that is comparable to  $d$ 's produced using traditional methods (e.g., repeated measures ANOVA). To examine the range of effect sizes that might be reasonable to expect in a future trial, we will calculate effect sizes and 95% confidence intervals for all of our primary and secondary outcomes.

The study will incorporate a 2 x 3 (Condition: RISE vs. information/referral x Time: pretreatment, post, and 1-month follow-up) mixed-factorial multi-measurement design producing  $N=60 \times 3$  time points = 180 measurement observations (or up to  $N=68 \times 3$  timepoints = 204). The intervention in this study is a difference over and above standard care (not in isolation), so it is expected that the effect will be modest ( $d=.5$ ,  $f^2=.15$ ,  $PV=.1$ ). Traditional approaches to repeated measures can thus be used to assess power. However, the design affords two alternate methods. The interaction term from the multilevel model will have 118 degrees of freedom, given the study design, which is more than sufficient to render a power = .95 for the primary outcomes. A simulation was also conducted leveraging the inputs from the prior studies, assuming a modest effect size, to determine power. In all simulated conditions, power is estimated  $>.80$  for primary outcomes. Consistent with the American Statistical Association recommendations, we will examine effect sizes and 95% confidence intervals, along with p-values in our tests.

We will assess the feasibility and acceptability of RISE and the comparison condition by looking for consistent patterns in rates of intervention attendance (i.e., number of RISE sessions attended) and reasons for RISE termination. We will examine the acceptability of both interventions using data from the CSQ-8 and qualitative data from patient interviews. Provider quantitative measures of feasibility and acceptability will be primarily

descriptive in nature, including mean summary scores and proportion of participants rating the intervention as feasible and acceptable. Lower scores will indicate a need to examine a given dimension more closely. We will integrate qualitative analyses within the quantitative analyses for the purposes of expansion, development, and convergence.

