**RISE.** The RISE will be delivered as per the refined manual, with its variable-length format (1 to up to 6 sessions within an approximate 10 week period). Following completion of the initial 60-minute RISE session, the provider and participant will determine whether they will have an additional session, and if so, it will be scheduled. Because RISE is specifically designed to be variable-length and patient-centered, it is possible that a participant may only desire to have 1 RISE session. Based on patient and provider feedback during Phase 2, all 6 of the RISE sessions can be up to 60 minutes. Originally, the subsequent sessions were intended to be 30-40 minutes, but that has proved infeasible. Both patients and providers have suggested that more time is allotted for subsequent sessions. Participants may have up to 6 RISE sessions in total. Intervention sessions will occur in private office space within primary care and/or mental health (e.g., Women’s Division of the National Center for PTSD). During times of unforeseen circumstances, such as the COVID-19 public health crisis of 2020, the clinical research sessions will be offered in telehealth format from the homes of licensed clinical psychologists [name] and [name], ensuring safe and private conditions for both the interventionists and the participants by following VA Boston’s and national VVC guidance for such clinical care. Individuals in the RISE condition will also complete the four brief validated self-report measures of empowerment, self-efficacy, patient activation, and valued action at the beginning of each RISE session to gauge treatment progress in real time and guide module selection, as we have done in Phase 2. Note these measures will be collected by the interventionist over the phone for any telehealth visits. This process takes approximately 10 minutes (leaving approximately 50 minutes for the RISE session). Participants will initially be emailed RISE intervention materials following their consenting/enrollment session, after which they will have the option to receive RISE intervention materials via USPS mail.

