**Female VHA Patient Assessments.** Data collection takes place throughout the study and is modeled after a prototypical Hybrid 1 trial . We will administer a full battery of psychosocial assessment at pre-treatment, post-treatment assessment (i.e., 10-weeks post enrollment), and 1 month follow-up (i.e., 14 weeks post-enrollment) described below under “Measures.” Participants in the RISE condition will also complete four brief measures of empowerment, self-efficacy, patient activation and valued action at the beginning of each RISE session. At the posttreatment and follow-up assessment, patients will complete a brief audio-recorded semi-structured interview about their experiences with their respective intervention. The post-treatment and follow-up assessments will either be conducted by phone or in person, depending on the participant’s preference (thus allowing for them to determine what is most safe and preferable for them). Women will be compensated with

\$25 for completing the pre-treatment assessment. Upon completion of the post-treatment assessment, women will receive \$50 in cash or by check for their time and participation. Upon completion of the follow-up assessment, women will receive a \$75 in cash or by check for their time and participation. A timeline of all measures is available below in Table 4.

Table 4. Timeline of Assessments	Pre	10-week	14-week
Demographics (age, race, sexual orientation, # deployments)	X		
Demographics (relationship status, housing status)	X	X	X
Personal Progress Scale	X	X	X
Patient Activation Measure- Short Form (PAM-13)	X	X	X
Valued Living Questionnaire (VLQ)	X	X	X
Center for Epidemiological Studies- Depression Scale (CES-D)	X	X	X
Health Service Use	X	X	X
The Conflict Tactics Scale-Revised (CTS-2)	X	X	X
PTSD Checklist for DSM-5 (PCL-5)	X	X	X
Patient Health Questionnaire- 15 (PHQ-15)	X	X	X
12-item Short Form Survey (SF-12)	X	X	X
Safety Behaviors Checklist (SBC)	X	X	X
Connor-Davidson Resilience Scale (CD-RISC 25)	X	X	X
Client Satisfaction Questionnaire 8 (CSQ-8)	X	X	X
Depression Anxiety Stress Scale- (DASS)	X	X	X
Coping Strategy Inventory-Short Form (CSI-SF)	X	X	X
Acceptability		X	X
IPV-Related Head Injury	X		

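### With visits at weeks 0, 10 and 14 coded 0, 1, 2, the single linear treatment x time term is in essence a baseline-to-week-14 comparison and gives no post-treatment effect

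*Combined protocol and SAP*

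**What the plan says.** Quantitative Data Analyses (Aim 3) sets the time codes: "Time will be coded as 0, 1, and 2 respectively for pretreatment, posttreatment, and 1-month follow-up". It gives them this meaning: "the Level-1 intercept will represent initial status and the Level-2 time coefficient will represent change over time". The arm indicator enters "as a predictor of the Level-1 change parameters (initial status and change over time) to evaluate the treatment x time interaction". The same paragraph also plans a model with "linear and quadratic polynomial contrasts and orthogonal contrasts to evaluate non-linear (i.e., non-constant) change". It names no covariance structure, no primary visit and no decisive term.

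The paragraph on Female VHA Patient Assessments fixes the visits: "post-treatment assessment (i.e., 10-weeks post enrollment), and 1 month follow-up (i.e., 14 weeks post-enrollment". The RISE paragraph under Randomization and intervention delivery allows "1 to up to 6 sessions within an approximate 10 week period", so the week-10 visit is the assessment placed at the close of the treatment window.

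On the use of the results, the analysis section says of its standardized effect that it will be comparable to those "produced using traditional methods (e.g., repeated measures ANOVA". It also wants the estimates "To examine the range of effect sizes that might be reasonable to expect in a future trial". Its second paragraph describes the design as two conditions by three time points.

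**The concern.** The gaps between visits are 10 and 4 weeks, but the codes make them equal. With equally spaced codes the middle visit sits at the mean of the time variable, where it has no leverage on a slope. The middle visit here is the post-treatment assessment. A single slope per wave therefore need not match the change in either interval. A reader could take it for the effect of RISE at the close of treatment, which it does not estimate.

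What is at stake is interpretation. The effect sizes are meant to inform expectations for a later trial, and a planner needs to know whether a given d refers to week 10, week 14 or neither.

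**Working it through.** **Inputs from the documents.** Codes 0, 1, 2; visits at weeks 0, 10, 14; 60 women with at least two assessments; d = .5; proportion of variance .1; 118 degrees of freedom; power .95.

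**Assumed.** 30 per arm, two-sided .05, unit SD at each visit, compound symmetry with correlation rho of .3, .5 or .7, complete data, and the effect trajectories below. The documents give none of these.

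**1. The plan's own figure.** No visit weights are stated. For the interaction term the plan gives 118 df and power .95. With f² = .1/.9 = .111 and noncentrality .111 x (1 + 118 + 1) = 13.3, the F test on 1 and 118 df has power .952, so .95 is reproduced. The df fit one linear time term and one interaction (180 - 60 - 2 = 118; a three-level visit factor leaves 180 - 60 - 4 = 116). But 118 is also 59 x 2, so this is consistent with a one-slope test and does not prove it.

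**2. Weights in the slope.** Least-squares weights are (t - mean t) / sum of (t - mean t)². For t = 0, 1, 2 the mean is 1 and the sum is 2, giving (-1, 0, 1)/2 = (-.5, 0, .5). Generalized least squares gives the same weights under a random intercept or a random slope with complete data. In mixed models fitted to simulated complete data, adding 5 units to every RISE value at week 10 left the interaction unchanged (.2294 before and after in one model type, .2120 in the other).

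**3. When the weight is not zero.**
- Week-14 value missing at random in an assumed 5%, 15% or 30% of women: the week-10 weight is about .01, .04 and .08 to .09.
- Unequal correlations (0-10 / 10-14 / 0-14) of .5/.6/.5 give -.08; .5/.7/.45 give -.19.
- Correlation decaying by week, with a 10-week correlation of .3/.5/.7, gives -.24/-.30/-.35.

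For comparison, the week-10 change itself has weights (-1, 1, 0).

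**4. What the slope shows, in SD units.**
- Steady weekly divergence to .50 at week 14: true gains are .50 x 10/14 = .36 and .50 x 4/14 = .14. The slope is .50/2 = .25 per wave, 30% below the first and 75% above the second.
- Effect (0, .5, .5): slope .25; the fitted line is .08, .33, .58.
- If d is taken as slope x 2 / SD (no formula is given), it is the week-14 d: .25 when the true effects are .5 at week 10 and .25 at week 14.

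**5. Power.** Normal approximation with variance c'Vc x 2/30. Example at rho = .5 for an effect of .5 at week 14: SE = sqrt(2 x .5 x 2/30) = .258, ratio 1.94, power .49. The 2-df test uses F on 2 and 116 df. Entries are for rho .3/.5/.7.

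| Arm difference at weeks 0, 10, 14 | Linear 0/1/2 (same as week-14 contrast) | Week-10 contrast | 2-df visit x arm |
|---|---|---|---|
| 0, .5, .5 | .37/.49/.71 | .37/.49/.71 | .37/.49/.72 |
| 0, .5, .25 | .13/.16/.24 | .37/.49/.71 | .28/.38/.59 |
| 0, .36, .5 | .37/.49/.71 | .22/.28/.43 | .30/.40/.62 |
| 0, 0, .5 | .37/.49/.71 | .05/.05/.05 | .37/.49/.72 |

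**6. The contrast model.** Intercept, linear and quadratic terms, each crossed with arm, make six mean parameters for 2 x 3 = 6 cells. That model is saturated, and its 2-df interaction test is the same under any time coding. Its single terms are not: the equally spaced orthogonal linear contrast is again proportional to (-1, 0, 1), while the raw linear term on 0, 1, 2 has weights (-1.5, 2, -.5).

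**The case against.** The strongest reply is that the plan already covers non-constant change. The polynomial and orthogonal contrasts come right after the coding sentence, and arm is then said to predict change parameters in the plural. On that reading the week-10 data are used in full. This stands in part: a reader might infer that the plan as a whole ignores week 10, and the documents do not support that. What remains is that the text spells out the change parameters only as initial status and change over time, and does not say whether the slope or the joint test decides.

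Second, coding by wave is defensible. RISE may be a single session and the comparator is one session, so many women may finish well before week 10, and a straight line in calendar weeks has no more support than one in waves. This stands. The slope is a valid average change per wave, and week 10 is the scheduled post-treatment assessment, not each woman's last session.

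Third, the zero weight is conditional. This also stands: no covariance is stated and some dropout is expected. It is a complete-data result for two common model types. The departures in step 3 are small or negative, and none yields a post-treatment effect.

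Fourth, a reader might infer that the coding costs power. The table does not support that as a general claim. The linear term equals the week-14 contrast throughout, beats the week-10 contrast when the effect grows or comes late, and loses when it fades.

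**Conclusion.** The point holds as a matter of estimand and interpretation. Under a random intercept or random slope with complete data, the stated treatment x time coefficient is exactly half the between-arm difference in baseline-to-week-14 change. Under the other covariances and dropout rates tried, its week-10 weight ran from -.35 to .09, and it is still not a post-treatment effect. In the illustrations it differs from the interval gains by 30% to 75%, or shows .33 at week 10 where the truth is .5; these sizes rest on assumed trajectories. Type I error is unaffected, and the direction of any power difference depends on a trajectory that the documents do not give. The planned contrast model would resolve the matter if arm is crossed with both terms and the decisive term is named; the text does neither explicitly. The change is worth making because it is cheap and the effect sizes are meant to guide a later trial. The plan's test is not invalid.

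**What to change.** In Quantitative Data Analyses (Aim 3), model visit as a three-level factor (baseline, week 10, week 14) crossed with arm, in line with the 2 x 3 design already described. Report the between-arm difference in change from baseline at week 10 and at week 14, each with a 95% confidence interval, and say which of these each d refers to. Name one primary contrast before the data are analysed. If the sponsor names week 14, the estimate in completers is twice the current slope, with the same power. If the polynomial model is kept, state whether arm is crossed with the quadratic term and which test decides.

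The cost is a wording change and a few lines of code, with no new visits or data. The downside is small: two estimates replace one slope, and no contrast has the most power under every trajectory, so the choice of primary contrast rests with the sponsor.

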#### **(c) Method and Data Analysis**

##### Aim 3

**Randomized clinical trial (RCT):** The goal of Aim 3 is to test the RISE intervention in comparison to an information/referral condition for women VA patients who have experienced past-year IPV. We selected a Hybrid Type 1 RCT design to evaluate the initial effectiveness RISE while gathering information on barriers and facilitators of implementation. We selected an information/referral comparison condition because a) this intervention is consistent with the current standard of care at the two study sites (and in the community); b) many other VA facilities are supposed to provide information and referrals for women who disclose IPV (according to VHA recommendations); and 3) an information/referral condition conforms to the US Preventive Services guidelines and to the suggestions of the Department of Health and Human Services. Participants will receive the information/referral condition for up to 60 minutes in order to standardize the comparison condition while also ensuring that women receive at least the minimum standard of care. At VA Boston, up to 68 female patients will be recruited and randomly assigned. Assuming 15% loss to follow-up based on current study estimates, we will aim to enroll 68 women to ensure sample size of n=60 for participants with post-treatment and/or follow-up assessments (i.e., at least 2 data points). To address our sub-aim, providers will be invited to participate in brief (30-minute), semi-structured qualitative interviews toward the end of the RCT to provide perspective on RISE implementation.

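### Letting arm predict initial status makes the main test a comparison of change: valid, but less precise than using the pre-treatment score already collected

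*Combined protocol and SAP*

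**What the plan says.** Quantitative Data Analyses (Aim 3) codes time 0, 1 and 2 for the three assessments and treats the pre-treatment score as the time-0 outcome. Arm enters "as a predictor of the Level-1 change parameters (initial status and change over time"), and the test of interest is the treatment x time interaction. A second model is planned: "We will also evaluate a model using linear and quadratic polynomial contrasts and orthogonal contrasts". Covariates are optional; the section speaks of "flexibility to assess and adjust for control variables, if needed (e.g., age, IPV frequency"). Randomization and intervention delivery adds demographic or relationship factors if the arms turn out to differ on them. Neither place names the pre-treatment score of the outcome as a covariate, and nothing in the document sets the two pre-treatment means equal.

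That score is available. The Female VHA Patient Assessments paragraph says "We will administer a full battery of psychosocial assessment at pre-treatment, post-treatment assessment" and again at 1-month follow-up, which is 14 weeks after enrollment.

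The analysis section says of its own method: "This analytic strategy will produce effective and efficient tests of change in outcomes, even in the presence of attrition". It plans effect sizes with 95% confidence intervals "To examine the range of effect sizes that might be reasonable to expect in a future trial". For power it states: "The interaction term from the multilevel model will have 118 degrees of freedom", and gives a power of .95.

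**The concern.** Under randomization the arms have the same expected pre-treatment mean. A model that estimates a separate mean for each arm spends information on a difference known to be zero in expectation. It then subtracts the chance difference in full, whatever the correlation between the first and later scores. Adjusting for the pre-treatment score, or fixing a common mean, subtracts only the part that the correlation supports.

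About 60 women are expected to be analysable, and the intervals are meant to inform a larger trial. If the pre-treatment score is not fully used, those intervals are wider and power is lower than the same data allow. No extra data collection would be needed.

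**Working it through.** **Inputs.** From the plan: 60 analysable women ((c) Method and Data Analysis), d=.5, PV=.1 and 118 degrees of freedom (Quantitative Data Analyses). Assumed because the plan does not state them: 30 per arm, two-sided .05 (suggested by the 95% intervals), complete data, SD 1 at every visit, and rho from .3 to .9.

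**1. The plan's own figure.** For a one-degree-of-freedom F test, PV=.1 gives f² = .1/.9 = .111. The noncentrality is 118 × .111 = 13.1 and power is .949, so the stated .95 reproduces. The same route with d=.5, where f² = .5²/4 = .0625, gives .77. The .95 therefore comes from PV=.1.

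**2. What the planned test measures.** Under compound symmetry the generalised least squares weights of the 0/1/2 slope on the three scores are −1/2, 0 and 1/2. The interaction is half the arm difference in change from pre-treatment to 14 weeks. Put on the 14-week scale, its variance is 2(1−rho) × 2/30. A model with free visit means and arm-specific initial status, which is what the polynomial contrasts span, gives the same variance.

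**3. Using the pre-treatment score.** A common pre-treatment mean with treatment x visit terms gives variance (1−rho²) × 2/30. The ratio to the plan is (1−rho²)/[2(1−rho)] = (1+rho)/2.

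**4. Random slopes, for illustration.** Add a slope variance of .10 of the baseline variance, uncorrelated with the intercept; rho here is the intercept's share of baseline variance. This adds .4 to the 14-week variance. The plan's variance becomes [2(1−rho)+.4] × 2/30 and the common-mean variance (1.4−rho²) × 2/30. At rho .5 these are .0933 and .0767, a ratio of .82.

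Power is for a 14-week effect of .5 baseline SD, by noncentral t with 118 df under compound symmetry (CS) and 58 df with random slopes (RS).

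| rho | Variance, plan (CS) | Variance, common mean (CS) | Ratio CS | Power CS | Ratio RS | Power RS |
|---|---|---|---|---|---|---|
| .3 | .0933 | .0607 | .65 | .368 to .521 | .73 | .295 to .384 |
| .5 | .0667 | .0500 | .75 | .484 to .602 | .82 | .363 to .427 |
| .7 | .0400 | .0340 | .85 | .698 to .767 | .91 | .478 to .515 |
| .8 | .0267 | .0240 | .90 | .859 to .893 | .95 | .567 to .589 |
| .9 | .0133 | .0127 | .95 | .990 to .993 | .98 | .691 to .698 |

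Under compound symmetry the 95% half-width, 1.98 × √variance, falls from .511 to .443 SD at rho .5 and from .323 to .307 SD at rho .8. To match the common-mean precision, the planned model would need 60/.75 = 80 women at rho .5 and 60/.90 = 67 at rho .8.

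**5. Validity.** In 10,000 simulated trials per setting, the change comparison rejected a true null in 5.3% (rho .5) and 5.2% (rho .7) of trials. Regression of the 14-week score on arm and baseline score rejected in 5.2% and 5.0%. Both were unbiased. The SD of the estimate was .259 against .226 at rho .5, and .201 against .186 at rho .7.

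**6. Sensitivity.** If the 14-week SD is k times the baseline SD, the ratio is k²(1−rho²)/(1+k²−2·rho·k). With k=1.2 this is .87 at rho .5 and 1.00 at rho .8, so the gain can vanish. With k=.8 it is .57 and .64. The plan says "Assuming 15% loss to follow-up based on current study estimates, we will aim to enroll 68 women". With 34 per arm and 15% giving baseline only, the compound-symmetry ratios are .69/.78/.87/.91 at rho .3/.5/.7/.8.

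**The case against.** The strongest reply is that nothing here is an error. Arm-specific initial status is a standard growth-model choice and matches the plan's question of whether arm moderates change. A reader might infer that the planned test is biased or invalid; the plan's text and the simulation do not support that.

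The size is also uncertain. Rho is not in the documents, the random-slope form (a fair reading of the Level-1 and Level-2 wording) roughly halves the power gain at rho .5, and at rho .9 almost nothing is left. Some women may have 10-week data only: if 15% give baseline only and a further 15% miss 14 weeks, the ratio is about .73 at rho .3, .82 at .5 and .93 at .8. All of this stands, and is why the result is given as a range.

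A simpler change would keep the linear slope and only fix a common mean. It is slightly more precise under compound symmetry (.73 at rho .5), but it mis-estimates the 14-week effect if change is not linear, which the plan itself allows for. The visit-level form, however, replaces one interaction with two effects, so a primary contrast must be named.

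Finally, a common mean assumes that baseline answers are unaffected by knowledge of allocation. Suppose knowledge shifted one arm by .2 SD at baseline only. The common-mean bias at 14 weeks would be −.2 × rho, against −.20 for the plan. If the shift persisted at every visit, the bias would be .2 × (1−rho), against 0 for the plan. A reader might infer that allocation was revealed too early. The documents conceal it until consent and place the questionnaires before the session, but do not say whether it is revealed between those steps. That is an open point, not a shown fault.

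**Conclusion.** The point holds as one of efficiency. The planned treatment x time test is valid but leaves precision unused. Over rho .3 to .9, the variance of the 14-week effect could fall to .65–.95 of the plan's under compound symmetry, or about .73–.98 with the illustrative random slopes. The gain is material at low to moderate rho, small at .8 or above, and can be nil if the 14-week SD exceeds the baseline SD. The figures rest on 30 per arm, complete data unless stated, and assumed correlations.

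A reader might set the planned-model powers in the table beside the plan's .95 and blame the handling of baseline. That would be wrong: the table uses d=.5, whereas the .95 reproduces from PV=.1.

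**What to change.** In Quantitative Data Analyses (Aim 3), and before arms are compared:

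- Make the main analysis a model with a common pre-treatment mean and treatment x visit terms at 10 and 14 weeks. Alternatively, adjust follow-up scores for the pre-treatment score of the same outcome.
- Name one primary contrast. The 14-week arm difference is the natural choice, since the planned linear test already targets it; the 10-week difference would be secondary.
- Report the planned model with arm-specific initial status as a sensitivity analysis.
- State whether allocation is revealed before the pre-treatment battery is complete, since the common-mean assumption depends on it.

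The cost is analysis text and code; no new data or visits are needed. The document is dated May 2020 and the trial window runs to about September 2020, so the change should be dated and recorded as made without sight of arm comparisons.
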